12.2 Amendments

A 'substantial amendment' is defined as an amendment to the terms of the METC application, or to the protocol or any other supporting documentation, that is likely to affect to a significant degree:

- the safety or physical or mental integrity of the subjects of the trial;
- the scientific value of the trial;
- the conduct or management of the trial; or
- the quality or safety of any intervention used in the trial.

All substantial amendments will be notified to the METC and to the competent authority.

Non-substantial amendments will not be notified to the accredited METC and the competent authority, but will be recorded and filed by the sponsor.

12.3 Annual progress report

The investigator will submit a summary of the progress of the trial to the accredited METC once a year. Information will be provided on the date of inclusion of the first subject, numbers of subjects included and numbers of subjects that have completed the trial, serious adverse events/ serious adverse reactions, other problems, and amendments.

12.4 Temporary halt and (prematurely) end of study report

The sponsor will notify the accredited METC and the competent authority of the end of the study within a period of 90 days. The end of the study is defined as the last patient's last visit.

The sponsor will notify the METC immediately of a temporary halt of the study, including the reason of such an action.

In case the study is ended prematurely, the sponsor will notify the accredited METC and the competent authority within 15 days, including the reasons for the premature termination.

Within one year after the end of the study, the investigator/sponsor will submit a final study report with the results of the study, including any publications/abstracts of the study, to the accredited METC and the Competent Authority.

12.5 Public disclosure and publication policy

Publication will be in accordance with the basic principles of Central Committee on Research involving Human Subjects (CCMO) statement on publication policy.

As described in the contract with MSD, the sponsor has full rights to publish the data unreservedly. This concerns both abstracts that are sent for presentation at conferences and manuscript for publication in high-impact peer-reviewed journals. The Amsterdam and Denver site will co-publish the data under the strong collaboration between PI [name] PI [name]. Please refer to the contract with MSD for details.

13. STRUCTURED RISK ANALYSIS

13.1 Potential issues of concern

Study medication

Participants will receive ertugliflozin 15 mg, an SGLT-2 inhibitor which is approved for blood-glucose lowering treatment in T2DM patients, and based on currently available data, is considered to be safe. Furthermore, SGLT-2 inhibitors may have other beneficial effects in general and are associated with a decrease in blood pressure and body weight. In large-sized cardiovascular outcome study, ertugliflozin was shown to have beneficial effects on cardiovascular outcomes and chronic kidney disease.

The most common adverse effects for ertugliflozin are genital mycotic infections and to a lesser extent pruritus, polyuria, frequent voiding and nycturia. However, genital mycotic infections usually occur after prolonged treatment, at least weeks. For canagliflozin, not ertugliflozin, increased amputations were reported in one study, but not in people with kidney disease, mostly in people that had previous amputations.

Hypoglycemia: SGLT2 inhibitors do not cause hypoglycemia as they do not increase insulin secretion. In people without diabetes, SGLT2 inhibitors do not cause hypoglycemia. When combined with drugs as insulin and sulfonylurea, SGLT2 inhibitors may cause hypoglycemia, particularly in people with normal eGFR.

Keto-acidosis: this has been reported in people with type 1 diabetes,²⁸ but is rare in people with type 2 diabetes with only a few cases reported worldwide.²⁸

Sodium diet:

Participants will undergo two periods of increased sodium intake (of 20 days each). While higher sodium intake, may increase blood pressure, it is usually not associated with adverse effects. Of note, sodium intake in the Netherlands is really high, therefore, for some people it may be their normal intake. Lowering sodium intake is not related to any health risk.

a. Level of knowledge about mechanism of action

Regarding side effects, they have a well-defined mechanism of action:

1. Genitourinary mycotic infections: due to SGLT2-induced glucosuria, urine provides a better culture media for mycotic infections.
2. Hypoglycaemia: higher risk in people with concomitant insulin therapy and/or sulfonylurea. Due to glucosuria, the amount of circulation can be inappropriate leading to hypoglycaemia.
3. Keto-acidosis: due to lowering of insulin concentrations due to glucosuria, and due to SGLT2-induced increment in glucagon concentrations, ketogenesis is enhanced. The nature of this mechanism facilitates clear actions to mitigate this effect as detailed below.

b. Previous exposure of human beings with the test product(s) and/or products with a similar biological mechanism

Please refer to the IB

c. Can the primary or secondary mechanism be induced in animals and/or in ex-vivo human cell material?

Please refer to the IB

d. Selectivity of the mechanism to target tissue in animals and/or human beings

Please refer to the IB

e. Analysis of potential effect

The dosage of 10 mg has good safety profile. Please refer to the IB.

f. Pharmacokinetic considerations

The dosage of 10 mg has good safety profile. Please refer to the IB.

g. Study population

The included participants are people with type 2 diabetes that are otherwise healthy. They are similar to the patients included in the ertugliflozin trials, making the effects on our population predictable.

h. Interaction with other products

Please refer to the IB

i. Predictability of effect

Please refer to the IB

j. Can effects be managed?

The most common side effect of SGLT2 inhibition therapy is genital mycotic infections. They occur usually after more chronic treatment. The incidence is increased 2.47-fold compared to placebo. However, a recent study in people with heart failure indicated that this may be reduced to 1.7% (incidence rate per 100 patient years 1.4) versus 0.7% in the placebo group

(incidence rate per 100 patient years 0.5) when proper instructions with respect to hygiene are provided, as will be done in our study. In addition, it is easily treated with a topical drug. The most feared side effect is euglycemic diabetic ketoacidosis (DKA). Due to lowering of endogenous or exogenous insulin levels, people with type 1 diabetes showed marked increases in euglycemic DKA despite controlled trial setting. For this reason, SGLT2 inhibitors are only in exceptional situations given to people with type 1 diabetes. In people with type 2 diabetes, euglycemic DKA is extremely rare, approximately 1 case per 1000 patient years. This likely concerns misclassified type 2 diabetes patients in whom insulin was stopped or reduced. To mitigate euglycemic DKA risk in our study, type 1 diabetes patients are excluded in our study, as well as individuals with diabetes and BMI <25 kg/m² as they phenotypically resemble type 1 diabetes patients. To prevent hypoglycemia, insulin dosages are lowered by the study team prior to initiation of the study drug if indicated. The study team consists of lead experts in the field of diabetology with ample experience in dosing glucose-lowering drugs. For the sodium diet we will monitor blood pressure when complaints are expressed by the study participant.

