There is no clear health benefit for the study participants, except that participation will provide insight into their sodium intake and knowledge how to reduce sodium intake to WHO-recommended amounts, which may benefit their long-term health. The short-term treatment with SGLT2 inhibitor ertugliflozin will not provide lasting benefits. On the other hand, the drug has little side effects, especially during short-term treatment, which will be closely monitored. The most commonly observed side effect (usually after more prolonged treatment) involves genital mycotic infections, which can easily be treated with antifungal topicals. Glucose levels and blood pressure are lowered during treatment. There are no health risks to short-term changes in sodium diet. Potential changes in blood pressure during the high-sodium diet are closely monitored. The study procedures are safe. There are no risks with undergoing MRI procedures and the use of iohexol and PAH to measure kidney hemodynamic function bears no risk, with >1500 tests carried out in our department. Burden of participants includes 5 visits (including screening); 4 visits where an MRI scan (duration 30 min) is performed and where 2 intravenous catheters are placed for tracer infusion during 2,5 hours; 13 24-hr urine collections and 5 24-hr blood pressure collections. A total of maximally 500 mL blood will be withdrawn over the course of a number of months. The study team will mitigate travel for the participants by collecting 24-hr blood pressure and 24-urine samples at home.

INTRODUCTION AND RATIONALE

Diabetic kidney disease (DKD) remains the leading cause of chronic kidney disease (CKD) and dialysis in the developed world, and a major cause of premature mortality. Sodium-glucose cotransporter 2 (SGLT2) inhibitors confer cardiovascular and renal protection in many, but not all people with type 2 diabetes (T2D) (1). Yet, the mechanisms of these salutary cardiorenal benefits remain unclear, and are incompletely explained by the modest improvements in blood pressure, glycemic control, body weight, and serum uric acid (2). A better understanding of the mechanism of cardio-renal protection in response to SGLT2 inhibition is therefore needed to determine which patients would see the greatest benefit from this drug class and also how to augment the beneficial effects with complimentary drugs and/or lifestyle changes such as changes in dietary sodium intake.

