From a metabolic point of view, the kidneys are highly active and are second only to the heart with respect to oxygen (O_2) consumption per tissue mass. To sustain this activity, the kidneys rely on various substrates to generate adenosine triphosphate (ATP) including citrate, glutamine, glucose and free fatty acids (FFA) (9). The vast majority of ATP consumption in the kidney relates to sodium reabsorption, and glucosuria and single-nephron hyperfiltration results in increased filtered sodium and activity of Na^+/K^+ ATPase pump due to high tubular glucose and sodium reabsorption (10-12). In fact, animal models suggest that renal O_2 consumption is increased by 40% in all cortical segments and by 160% each in the S3 segment and medullary collecting duct (13-17). In animal models, SGLT2 inhibition attenuates single-nephron hyperfiltration (18) and have also been shown to improve renal oxygenation and ameliorate renal hypoxia (19). Thus the SGLT2-induced renal benefit may be driven by improvements in renal oxygen availability. In addition, changes in tubular sodium reabsorption increase renal EPO production, which, through enhanced erythropoiesis, is the most likely explanation for the increase in hematocrit.

Thus, whether SGLT2 inhibitors modulate natriuresis or not, changes in tubular sodium handling lead to reduction of hyperfiltration, renal oxygen consumption and enhanced EPO secretion that collectively are thought to drive beneficial cardiorenal outcomes, amongst several hypotheses; effects that may be dependent of the amount of dietary sodium intake as argued below.

SGLT2 inhibitors may alter other aspect of sodium homeostasis as well. People with T2D are known to be sensitive to excess sodium intake, which may results in extracellular volume (ECV) expansion and hypertension. This is different for healthy, lean people in whom

increased salt intake usually does not increase blood pressure. These individuals are termed sodium-resistant (20,21). High-sodium intake suppresses SGLT2 expression leading to natriuresis. An effect not observed in rodents with hyperglycemia (22). Thus, SGLT2 inhibition during high-sodium diet could restore this response.

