After confirmation of eligibility during screening, a 24-hr blood pressure measurement as well 24-hr sodium excretion is measured prior to the dietary blocks as detailed below. This 24-hr sodium and blood pressure measurement will be crucial for hypothesis 2. Urine containers and 24-hr blood pressure meters are provided to the patient and collected after recording.

Screening	Day 0	Day 1 (offered at home of participants to reduce travel)
Medical history	X	
Physical examination	X	
Review of medication	X	
Office blood pressure	X	
Routine hematology and chemistry	X	
HbA1c	X	
Urinary dipstick	X	
Start 24-hr urine sodium collection	X	
Start 24-hr BP measurement	X	
Return 24-hr urine sodium collection		X
Return 24-hr BP measurement		X

Subsequently, 4 of the blocks of 20 days below are conducted in random order with differences in study medication (placebo versus ertugliflozin) and sodium diet (90 mmol/day versus 250 mmol/day). The washout is 4 weeks between the blocks. Please refer to the figure on page 11. Urine containers are provided to the patients.

A sodium diet is commenced (either aimed at 90 mmol/day or 250 mmol/day) and it is expected that after 10 days this is reached (+/- 20%, due to normal variation in sodium excretion). This will be assessed with two 24 hour urine collections. Subsequently, the diet is continued and treatment with the study medication commences. In the morning of day 9, 24-hour blood pressure recording starts. At the study visit at day 10 of treatment, endpoints are collected following an overnight fast of 10-hours at our clinical trial unit as indicated below. A flow chart of study activities is attached below.

Subject will arrive at Amsterdam UMC location AMC for multimetric MRI following an overnight fast. Subjects are then brought to Clinical Research Unit (CRU) location VUMC where the 24-hour urine collection is processed (in order to assess sodium

excretion and other variables of interest obtained from 24-hr urine collection). The 24-hour blood pressure recording is stopped. Two intravenous catheters will be placed in both forearms for blood sampling and for the administration of test-agents (e.g. iohexol and PAH). A total of 125 mL blood will be drawn during the day for this purpose. The renal protocol commences with measurement of GFR and effective renal plasma flow (ERPF) based on continuous infusion for 2.5.

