During the infusion, several measurements will be performed including anthropometrics, bio-impedance analysis, blood pressure measurement and collection of samples for biomarker analysis.

	Day -10	Day -2	Day -1	Day 0	Day 3	Day 10
Start sodium-diet (continue until day 10)	X					
24-hr urine sodium (compliance)		X	X			
Start study medication (continue until day 10)				X		
Telephone call compliance					X	
Recent history						X
24-hr blood pressure						X
Measured GFR						X
ERPF						X
Intrarenal hemodynamic function						X
Office blood pressure						X
Hematocrit						X
Renal oxygenation (BOLD MRI)						X
RAAS components						X
Collection of biomarkers						X
Body anthropometrics						X
24-hr urine analysis (sodium, UACR)						X

Efficacy measurement more detailed:

- 1) **Height.** A height measuring board will be used to assess height. Patients will be asked to remove their footwear and headgear and to stand on the board with their feet together, heels against the back board and knees straight. The patient should be looking straight ahead, without tilting the head up, with eyes and ears at the same level. The measure arm will gently be moved down onto the head of the participant and height will be read in centimeters at the exact point.
- 2) **Weight.** Body weight will be recorded by a digital calibrated weighing scale on a firm, flat surface. Patient will be asked to remove their footwear, extra layers of clothing, jewelry and any items in his/her pockets before standing still on the weighing scale with arms placed on the side. Measurement will be recorded on the Case Report Form (CRF) to the nearest kilogram. No deduction for clothing will be permitted.
- 3) **Body Mass Index (BMI).** BMI will be derived from height and bodyweight by using the mathematical formula: $BMI = [kg/[m]^2]$.
- 4) **Waist circumference.** A constant tension tape will assess waist circumference with the patient in a standing position with the arms relaxed at the sides and without clothing, that is, directly over the skin. Measurement will be performed at the midpoint between the lower margin of the last palpable rib and the top of the iliac crest at the end of a normal expiration.

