11.3 Benefits and risks assessment, group relatedness

All participants will receive ertugliflozin, an SGLT-2 inhibitor which is approved for blood-glucose lowering treatment in T2DM patients. Based on currently available data from thousands of patient years, the drug has shown to be safe. In addition to glucose-lowering, SGLT-2 inhibitors have other beneficial effects, by inducing a decrease in blood pressure and body weight for instance. Clinically, SGLT2 inhibitors prevent kidney function decline, hospitalization for heart failure and cardiovascular events after longer-term use.

SGLT2 inhibitors have side effects. The most common side effect are genital mycotic infections, which can be treated with a topical antimycotic crème. Other side effects include polyuria, frequent voiding and nycturia.

As in all drug intervention trials, in this study, we will closely monitor patients for adverse drug and study events. Participants can contact the research staff 24 hours a day. It should be noted that most of these side effects rarely occur in such a short treatment duration as in the current study. There is no risk of a short-term change in sodium diet on long-term health outcomes. In addition, effects of high-sodium diet [e.g. on blood pressure] are closely monitored.

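### The protocol says blood pressure on the high-sodium diet is watched closely, but schedules no reading in the first 19 of 20 diet days and sets no action limit

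*Combined protocol and SAP*

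**What the plan says.** Two places promise close observation. The Summary, under burden and risks, states: "Potential changes in blood pressure during the high-sodium diet are closely monitored". Section 11.3 repeats it: "In addition, effects of high-sodium diet [e.g. on blood pressure] are closely monitored". Section 13.1, item j, which asks whether effects can be managed, says instead: "For the sodium diet we will monitor blood pressure when complaints are expressed by the study participant".

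The schedule in Section 8.3 gives, for each block:

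- Day -10: "Start sodium-diet (continue until day 10".
- Days -2 and -1: 24-hour urine sodium for compliance.
- Day 0: study drug starts.
- Day 3: a telephone call about compliance.
- Day 9: "In the morning of day 9, 24-hour blood pressure recording starts".
- Day 10: the clinic visit, with office blood pressure. Of the ambulatory device: "The 24-hour blood pressure recording is stopped".

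The Summary counts five visits including screening, and "13 24-hr urine collections and 5 24-hr blood pressure collections".

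On limits, Sections 4.2 and 4.3 contain no upper blood pressure value. Sections 5.3 (escape medication) and 8.4.1 (specific withdrawal criteria) are both marked as not applicable. Section 4.2 admits hypertensive participants on stable treatment, up to age 85. Section 4.3 admits participants on diuretics only if these can be stopped for the study.

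**The concern.** The three statements do not describe the same plan, and the schedule supports the weakest of them. A rise in blood pressure is the response the protocol itself expects. The Introduction says: "People with T2D are known to be sensitive to excess sodium intake, which may results in extracellular volume (ECV) expansion and hypertension", and the secondary objective in Section 2.2 calls the effect of the diet hypertensive. A rise need not cause symptoms, so a check that waits for a complaint can miss it. The participants with most to lose are treated hypertensives who have given up a diuretic.

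What is at stake is participant safety and the accuracy of the risk description, not the efficacy analysis.

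**Working it through.** **1. Reproduce the plan's diet length.** Diet start is day -10 and the visit is day 10 (Section 8.3): 10 - (-10) = 20 days. This matches the 20 days per block in Section 5.2.

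**2. Time to the first scheduled reading.** 9 - (-10) = 19 days, and 19/20 = 95% of the diet period. The recording is stopped at the day 10 visit, when the diet ends, so its full result cannot guide action during the diet. A value might be seen when the device is fitted on day 9, but that leaves one day and no rule for acting.

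**3. Could a reading be hidden in the missing design figure?** The Summary's burden counts can be rebuilt from the schedule:

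| Item | From the schedule | Summary |
|---|---|---|
| Visits | 1 screening + 4 blocks x 1 = 5 | 5 |
| 24-hour blood pressure recordings | 1 + 4 x 1 = 5 | 5 |
| 24-hour urine collections | 1 + 4 x 3 = 13 | 13 |

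All three agree, so there is no unlisted visit or recording in which a mid-diet check could sit. The other readings in Section 8.3, during the MRI and the tracer infusion, also fall on day 10.

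**4. Extent.** High-sodium blocks: 34 x 2 = 68. Diet days: 68 x 20 = 1,360. Days before the first scheduled reading: 68 x 19 = 1,292 (95%). Exposure is not uniform: in one of each participant's two high-sodium blocks, the last 10 days are on ertugliflozin, which is 34 x 10 = 340 days (340/1,360 = 25%).

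**5. Size of the sodium change.** Section 4.2 requires baseline intake below 200 mmol/day. The target of 250 is therefore at least 50 mmol/day higher (50/200 = 25%), and 80 higher than the usual 170 (80/170 = 47%). This concerns the target only. Section 8.3 expects it to be reached within 20%, that is 250 x 0.8 = 200 to 250 x 1.2 = 300 mmol/day.

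**6. Effect of one added reading on day -1.** It falls -1 - (-10) = 9 days into the diet and leaves 10 - (-1) = 11 days to act. Days before the first reading drop from 1,292 to 68 x 9 = 612 (612/1,360 = 45%).

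**The case against.** The best defence is that exposure is short, the population is selected and other safeguards exist. Section 4.3 excludes acute coronary syndrome, symptomatic heart failure and stroke or transient ischaemia within six months, as well as unstable renal disease. Section 4.2 requires eGFR 60-90 and stable RAS inhibition, or another antihypertensive, in hypertensive participants. A person whose diuretic cannot be stopped is not enrolled. Office and 24-hour pressures are taken at screening. Section 11.3 offers contact at any hour, and Section 8.4 lets the investigator withdraw a participant on clinical judgement. Section 9.2.2 records that the ethics committee agreed the study is low-risk. The 24-hour result from a first high-sodium block is also available before a second one starts, because at least four weeks of washout intervene.

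All of this stands and bears on how serious the gap is. It does not make the monitoring close. Contact at any hour still depends on a complaint, and judgement needs a reading to act on.

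Three stronger readings are tempting and should be resisted:

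- A reader might infer that a known number of participants will have a large rise. The documents give no expected rise on the diet, so any such count would rest on assumed values.
- A reader might infer that every participant will actually eat more sodium than before. Only the target guarantees that; someone just below 200 mmol/day at entry could comply at 200 with almost no change.
- A reader might infer that the ethics committee was misled. The same protocol contains the schedule and the plain statement in Section 13.1. The fair description is an internal inconsistency.

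**Conclusion.** The point holds. The protocol twice claims close blood pressure monitoring on the high-sodium diet, yet schedules none for 19 of 20 days in each of 68 blocks, relies on complaints in between, and sets neither an entry ceiling nor an action limit. This follows from the protocol's own day numbers and burden counts. It assumes only that the missing figure adds no reading, which those counts support.

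The size is that of a correctable safety gap in a selected population with some protection already in place. The documents show neither that harm is likely nor how large a rise to expect. The sample size and the primary interaction analysis are unaffected.

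**What to change.** 1. **Section 8.3 schedule:** add one seated reading on day -1 of each high-sodium block, alongside the 24-hour urine collection and before the first tablet. It precedes study drug, so it reveals nothing about allocation in that block.
2. **Section 8.4.1:** replace the not-applicable entry with a confirmed systolic/diastolic limit chosen by the investigators, and state the action: end that diet block.
3. **Section 4.3:** add a blood pressure ceiling based on the screening readings, taken or repeated after any diuretic has been stopped. The protocol does not say whether diuretics are already stopped at screening.
4. **Summary, Sections 11.3 and 13.1:** describe this one plan in all three places.

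A home reading at the day 3 call is better left out. It is on drug, and a change from day -1 reported to staff could hint at allocation. If it is wanted, it should report only whether the limit is exceeded.

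**Cost.** 34 x 2 = 68 short readings. The Summary has the team collecting urine at home to spare travel, so no clinic visit should be needed. If staff are not present on day -1, a home device is required. Sample size and endpoint timing do not change.

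**Downside.** A few blocks would be stopped for high blood pressure, probably more often on high-sodium placebo. Those participants would leave the per-protocol set (Section 10.1) and be replaced (Section 8.5), which could bias the interaction. Report such stops by condition, and keep those participants' other blocks in a sensitivity analysis.
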